Appendix K Response Evaluation Criteria for Non-Hodgkin Lymphoma

Disease response assessment will be evaluated using the revised Lugano 2014 Classification for NHL ([Cheson et al 2014](#)).

Response assessments will be done by the Investigators following the revised Lugano 2014 Classification response criteria ([Cheson et al 2014](#)).

Tumour assessment will be made for target lesions (ie, measurable disease), non-target lesions (ie, non-measurable disease), organ enlargement (eg, spleen, liver), and new lesions on CT and combined with visual assessment of PET-CT for response assessment ([Cheson et al 2014](#); [Table K35](#)).

K 1 Visual Interpretation of PET-CT Scans

Variation in FDG uptake in a nodal or extranodal sites indicative for lymphoma will be visually assessed using the Deauville 5-point scale.

Target Lesions

Up to a maximum of 6 dominant, measurable lymph nodal or extranodal lesions should be assessed as target lesions and documented at baseline and throughout the study.

A lesion will be considered measurable if:

- For nodal lesions: $LDi > 1.5$ cm
- For extranodal lesion: $LDi > 1$ cm

Lesions visible on PET but not on CT/MRI to be assigned as non-target lesions.

Target nodal or extranodal lesions nodes should be selected according to all of the following:

- They should be clearly measurable in at least 2 perpendicular dimensions
- If possible, they should be from disparate regions of the body
- They should include mediastinal and retroperitoneal areas of disease whenever these sites are involved

The perpendicular long and short axis diameters will be measured and recorded in the transverse plane at baseline and follow-up.

For the selected target lymph nodal lesions, the sum of the product of the perpendicular diameters will be calculated with the percentage change from baseline for assessment of response and nadir for assessment of progression.

Non-target Lesions

All other lesions (including nodal, extranodal, and assessable disease) not selected as target lesions, as well as truly non-measurable sites of disease should be followed as non-measurable disease (eg, cutaneous, gastrointestinal, bone, spleen, liver, kidneys, pleural or pericardial effusions, ascites) and should be factored into the overall response assessment. Non-target lesions will be documented at baseline and throughout the study. Measurement of these lesions is not required to be documented on the eCRFs.

Spleen Involvement

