Spleen will be considered to be normal if size of its vertical length (cranial-caudal measurement) is ≤ 13 cm. For patients with splenomegaly at baseline, spleen vertical length will be assessed at screening and all subsequent response evaluations.

Liver Involvement

Intrahepatic lesions should be considered as target, non-target, or new lesion as applicable. The presence of a diffuse or focal uptake with or without focal or disseminated nodules support liver involvement. Given variability in body habitus and the impact of numerous medical conditions, liver size by physical examination or CT scan is not a reliable measure of hepatic involvement by lymphoma. For these reasons, liver size will not be collected in eCRFs.

Bone Marrow Involvement

Bone marrow involvement by lymphoma documented by aspirate and/or biopsy will be reported on the eCRF as present or absent.

Table K35 Response Assessment Criteria for Non-Hodgkin Lymphoma

Response and site	PET-CT-based response	CT-based response
Complete response:	Complete metabolic response:	Complete radiologic response – all of the following:
Lymph nodes and extralymphatic sites (target lesions)	Score 1, 2, or 3 ^a with or without a residual mass on 5PS ^b	Target nodes/nodal masses must regress to ≤ 1.5 cm in LD _i . No extralymphatic sites of disease (0 \times 0 cm)
Non-measured lesion (non-target)	Not applicable	Absent/normal
Organ enlargement	Not applicable	Regress to normal; spleen vertical length is ≤ 13 cm
New lesions	None	None
Bone marrow	No evidence of FDG-avid disease in marrow	Normal by morphology; if indeterminate, IHC negative

Table K35 Response Assessment Criteria for Non-Hodgkin Lymphoma

Response and site	PET-CT-based response	CT-based response
Partial response:	Partial metabolic response:	Partial remission – all of the following:
Lymph nodes and extralymphatic sites	Score 4 or 5 ^b with or without a residual mass on 5PS	≥ 50% decrease in SPD of up to 6 target measurable nodes and extranodal sites
Non-measured lesion	Not applicable	Absent/normal, regressed, but no increase
Organ enlargement	Not applicable	Spleen must have regressed by > 50% in length beyond normal
New lesions	None	None

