Bone marrow	Residual uptake higher than uptake in normal marrow but reduced compared with baseline (diffuse uptake compatible with reactive changes from chemotherapy allowed). If there are persistent focal changes in the marrow in the context of a nodal response, consideration should be given to further evaluation with MRI or biopsy or an interval scan	Not applicable
No response or stable disease:	No metabolic response:	Stable disease:
Target nodes/nodal masses, extranodal lesions	Score 4 or 5 with no significant change in FDG uptake from baseline at interim or end of treatment	< 50% decrease from baseline in SPD of up to 6 dominant, measurable nodes and extranodal sites; no criteria for progressive disease are met
Non-measured lesions	Not applicable	No increase consistent with progression
Organ enlargement	Not applicable	No increase consistent with progression
New lesions	None	None
Bone marrow	No change from baseline	Not applicable

Table K35 Response Assessment Criteria for Non-Hodgkin Lymphoma

Response and site	PET-CT-based response	CT-based response
Progressive disease:	Progressive metabolic disease:	Progressive disease requiring at least 1 of the following:
Individual target nodes/nodal masses	Score 4 or 5 with an increase in intensity of uptake from visually determined nadir and/or	
PPD progression:
 
An individual node/lesion must be abnormal with:
 
 • LDi > 1.5 cm AND • Increase by \geq 50% from PPD nadir AND • An increase in LDi or SDi from nadir 
 ◦ 0.5 cm for lesions \leq 2 cm ◦ 1.0 cm for lesions $>$ 2 cm 
In the setting of splenomegaly, the splenic length must increase by $>$ 50% of the extent of its prior increase beyond baseline (eg, a 15 cm spleen must increase to $>$ 16 cm). If no prior splenomegaly, must increase by at least 2 cm from baseline

Non-measured lesions	None	New or clear progression of pre-existing non-measured lesions
New lesions	New FDG-avid foci consistent with lymphoma rather than another aetiology (eg, infection, inflammation). If uncertain regarding aetiology of new lesions, biopsy or interval scan may be considered	
 • Regrowth of previously resolved lesions • A new node $>$ 1.5 cm in any axis A new extranodal site $>$ 1.0 cm in any axis; if $<$ 1.0 cm in any axis, its presence must be unequivocal and must be attributable to lymphoma • Assessable disease of any size unequivocally attributable to lymphoma

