5PS = Deauville 5-point scale; CT = computed tomography; FDG = fluorodeoxyglucose; GI = gastrointestinal; IHC = immunohistochemistry; LDi = longest transverse diameter of a lesion; MRI = magnetic resonance imaging; PET = positron emission tomography; PPD = cross product of the LDi and perpendicular diameter; SDi = shortest axis perpendicular to the LDi; SPD = sum of the product of the perpendicular diameters for multiple lesions.

K 2 Assessment of New Lesions

Appearance of any new lesions > 1.5 cm in any axis during or at the end of therapy, even if all other lesions are decreasing should be considered progression. Increased FDG uptake in a previously unaffected site should only be considered progression after confirmation with other modalities (eg, CT, MRI, biopsy).

In patients with no history of pulmonary lymphoma, new nodules identified by CT are benign and should be considered negative for lymphoma. These lesions typically represent infectious or inflammatory lesions; therefore, if FDG positive, should not be considered positive for lymphoma in the absence of confirmatory tests, (eg, histology).

The presence or absence of new lesions will be recorded in the eCRF.

K 3 Overall Response Assessment

The efficacy endpoints are based on the overall response assessment, which is combining the radiological response from PET/CT scans, the bone marrow findings (if applicable) and any additional clinical finding, including cytologic or histopathologic findings for each disease response assessment during the study. The possible outcomes for ORR as CR, PR, SD, PD, Unknown. The Investigator-assessed ORR and respective date will be captured on the eCRF.

K 4 References

Cheson et al 2014

Appendix L Changes Related to Mitigation of Study Disruptions Due to Cases of Civil Crisis, Natural Disaster, or Public Health Crisis

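### Table K35's PET-CT rule for nodal partial response requires no fall in uptake, so unchanged score 4 or 5 disease meets both partial response and no metabolic response

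*Protocol*

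**What the plan says.** Protocol section 8.1.3.1 has response assessed by the revised Lugano 2014 criteria as set out in Appendix K, and bases the primary and secondary endpoints on the investigator's overall response. Table K35 gives a PET-CT column and a CT column for each category.

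- **Partial response, PET-CT** (headed "Partial metabolic response"). Nodes and extralymphatic sites: score 4 or 5 "with or without a residual mass on 5PS". The same words appear earlier in the complete-response row; the cell at issue is the one in the partial-response block. Marrow: "Residual uptake higher than uptake in normal marrow but reduced compared with baseline".
- **No response or stable disease, PET-CT.** Nodes and extranodal lesions: "Score 4 or 5 with no significant change in FDG uptake from baseline at interim or end of treatment".
- **Progressive disease, PET-CT.** Score 4 or 5 with uptake up from the visual nadir, and/or new avid foci.
- **CT column.** Partial response needs an SPD fall of at least 50%. Stable disease is a smaller fall, with the condition that "no criteria for progressive disease are met".

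On how the two columns are joined, the introduction to Appendix K lists target lesions, non-target lesions, organ enlargement and "new lesions on CT and combined with visual assessment of PET-CT for response assessment". Section K 3 describes the overall response as one "which is combining the radiological response from PET/CT scans", together with marrow and clinical findings. SAP section 5.2.1.1 counts CR or PR before any evidence of progression and states that a response need not be confirmed.

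**The concern.** The line between partial response and stable disease decides who counts as a responder. In the PET-CT column that line is missing for nodal and extralymphatic disease, because one category contains the other. An investigator who applies the partial-response cell literally can record PR for a patient whose uptake has not changed.

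One such read is enough. It makes the patient a responder for ORR and sets the start of DoR and the value of TTR. Best response is carried across visits, so a later stable-disease read does not undo it. The planned ORR sensitivity analysis (SAP section 5.2.1.3) changes the analysis set and keeps the same reads. Independent central review is optional, at the Sponsor's discretion (protocol section 8.1.2).

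**Working it through.** The plan gives no figure to reproduce here. The check is a comparison of definitions.

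**Step 1: the two nodal PET-CT cells.** Partial response = {score 4 or 5}. No metabolic response = {score 4 or 5, no significant change from baseline}. The second set is a subset of the first.

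**Step 2: the other PET-CT rows.** Non-measured lesions and organ enlargement are marked not applicable in both blocks, and new lesions must be absent in both. Only the marrow row differs (reduced against unchanged), and it separates the categories only where marrow uptake is abnormal. Footnote b defines scores 4 and 5 as uptake above liver; neither footnote a nor footnote b adds a condition on change.

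**Step 3: all uptake patterns.** For a patient at score 4 or 5 with no new lesion and no abnormal marrow uptake, the nodal cells give:

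| Uptake | Categories met as written |
|---|---|
| Reduced from baseline, no rise from nadir | Partial response |
| Unchanged from baseline, no rise from nadir | Partial response and no metabolic response |
| Fell, then rose back to baseline | Partial response, no metabolic response and progression |
| Fell, then rose part of the way | Partial response and progression |
| Above baseline | Partial response and progression |

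Scores 1 to 3 fall under complete response. The second line is the one that matters most for ORR. The overlaps with progression matter less, because SAP section 5.2.1.1 counts only responses before any evidence of progression.

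**Step 4: is there a tie-break?** Appendix K and K 3 say only that PET and CT are combined. Protocol section 9.4.2 and SAP section 5.2.1 add no rule. The one explicit PET/CT rule, in protocol section 8.1.2, concerns complete response: a new CT-based CR should be confirmed by a negative PET. Nothing equivalent covers partial response against stable disease.

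**Step 5: is the column in use when ORR is read?** Inclusion criterion 6 requires an FDG-avid lesion except in MZL. Protocol section 8.1.2 and Table 14 make PET mandatory at Week 8. The interim (protocol sections 10.9.2 and 10.9.5) is taken once patients could complete 2 cycles: 2 × 28 days = 56 days = 8 weeks. The first PET visit is therefore the interim response visit for Cohorts B1 and B2. MZL patients with non-avid lesions need only CT and are outside the overlap.

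**The case against.** The best defence is that nobody would read the table this way. The block is headed partial metabolic response, and unchanged uptake is named only under the other heading. Section K 1 says that variation in uptake is what is assessed. For target nodes, "the sum of the product of the perpendicular diameters will be calculated with the percentage change from baseline for assessment of response". Week 8 has a CT as well, and CT partial response needs a 50% fall. The table is adapted from a published classification that may settle the point. All of this makes a misread less likely, and it confirms that a reduction is meant. None of it is a stated rule, and the cited source cannot be checked from the documents.

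A second defence reads the marrow row strictly: a patient with normal, unchanged marrow fails the partial-response marrow cell and is therefore stable disease. That reading would deny a PET partial response to every marrow-negative responder, so it cannot be intended and does not rescue the table.

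A reader might go further and infer that ORR will be inflated, perhaps by counting PET visits or by noting that each reclassified patient adds 1/n. The documents do not support this. Visit counts are not patients misread, 1/n holds for any misclassification, and the cohort sizes are redacted. A reader might also infer that PET should override CT. The plan does not say so. Such a rule could raise ORR, by counting PET partial response with CT stable disease, and it would not fully match the CR confirmation rule in section 8.1.2.

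**Conclusion.** The concern holds as a defect of definition. As written, unchanged score 4 or 5 uptake with no new lesion and no abnormal marrow uptake meets both partial response and no metabolic response, and no text decides between them. This is a wrong rule in the definition of the Part B primary endpoint, since it admits a non-responder as PR.

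The effect on ORR cannot be sized. It lies between zero, if readers follow the stable-disease cell or the CT, and the unknown share of patients in the overlap. The conclusion rests on the table text, the absence of a tie-break, and investigator reads being used unconfirmed. It does not rest on any assumed cohort size or misread rate.

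**What to change.** 1. In the nodal and extralymphatic PET-CT cell for partial response, require uptake to be reduced from baseline, as the marrow cell already does.
2. In the no-metabolic-response PET-CT cell, add the clause in its CT neighbour: "no criteria for progressive disease are met".
3. Carry that same clause into the partial-response PET-CT cell. Items 1 and 2 separate partial response from no metabolic response, and no metabolic response from progression. Uptake that fell and then rose part of the way would still be both reduced from baseline and up from nadir, so full separation of the three categories needs the clause in both cells.
4. Tell sites by memo, and say there that reduced is to be read as the opposite of no significant change, so that a trivial fall does not meet both cells.

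The cost is a few clauses in one table and a memo. No extra scans and no change to the SAP's analyses are needed. Reported ORR may be slightly lower, and whether uptake is reduced remains a visual judgement.

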Appendix M Disease Prognostic Scores

M 1 Follicular Lymphoma Prognostic Scores

Table M36 FLIPI-1 Criteria

Category	Risk Factor
Age	≥ 60 years
Ann Arbor Stage	III-IV
Haemoglobin level	< 12 g/dL
Serum LDH level	$>$ ULN
Number of nodal sites	≥ 5
Risk Group According to FLIPI Chart	Number of Factors
Low	0-1
Intermediate	2
High	≥ 3

FLIPI: follicular lymphoma international prognostic index; LDH: lactate dehydrogenase; ULN: upper limit of normal.

Source: [\(Solal-Célyny et al 2004\)](#)

Table M37 FLIPI-2 Criteria

Risk Factors	
Age	
Raised beta-2-microglobulin	
Haemoglobin < 12 mg/dL	
Longest diameter of largest involved node ≥ 6 cm	
Bone marrow involvement	
Risk Category and Prognosis	
FLIPI-2 Score	FLIPI-2 Risk Category
0	Low
1-2	Intermediate
3-5	High

FLIPI: follicular lymphoma international prognostic index.

Source: [\(Solal-Célyny et al 2004, Federico et al 2009\)](#)

M 2 Mantle Cell Lymphoma Prognostic Score

Table M38 Simplified MIPI

Point	Age	ECOG	LDH ULN	WBC (10 ⁹ /L)
0	<50	0-1	< 0.67	< 6.700
1	50-59	-	0.67-0.99	6.700-9.999
2	60-69	2-4	1.000-1.49	1.000-14.999
3	≥70	-	≥ 1.5000	≥ 15000

ECOG: Eastern Cooperative Oncology Group; LDH: lactate dehydrogenase; MIPI: Mantle cell lymphoma International Prognostic Index; ULN: upper limit of normal; WBC: white blood cell.

Source: [\(Hoster et al 2008\)](#)

Table M39 Risk Category According to the MIPI

MIPI Score	Risk
0-3	Low
4-5	Intermediate
6-11	High

MIPI: Simplified Mantle cell lymphoma International Prognostic Index.

Source: [\(Hoster et al 2008\)](#)

M 3 Diffuse Large B-cell Lymphoma Prognostic Score

Table M40 International Prognostic Index

Category	Risk Factor
Age	> 60 years
Ann Arbor Stage	III-IV
Performance status	2-4
Serum LDH level	> ULN
Extranodal sites	> 1
Risk Group According to IPI Chart	Number of Factors
Low	0-1
Low-intermediate	2
High intermediate	3
High	4-5

LDH, lactate dehydrogenase

Source: [International Non-Hodgkin's Lymphoma Prognostic Factors Project, NCCN Guidelines](#)

M 4 References

Federico et al 2009

Hoster et al 2008

Appendix N Abbreviations

Abbreviation or special term	Explanation
AE	adverse event
AESI	adverse event of special interest
ALT	alanine aminotransferase
ANC	absolute neutrophil count
AST	aspartate aminotransferase
Bcl-2	B-cell lymphoma 2
Bcl-xL	B-cell lymphoma-extra large
BCRP	breast cancer resistance protein
B-NHL	B-cell non-Hodgkin lymphoma
CAR-T	chimeric antigen receptor T cell
cfDNA	circulating free deoxyribonucleic acid
CFR	Code of Federal Regulations
CI	confidence interval
C _{max}	maximum observed concentration
CMV	cytomegalovirus
CNS	central nervous system
COVID-19	coronavirus disease 2019
CR	complete response
CRO	contract research organisation
CSP	clinical study protocol
CSR	clinical study report
CT	computed tomography
CTCAE	Common Terminology Criteria for Adverse Events
ctDNA	circulating tumour deoxyribonucleic acid
CTEP	Cancer Therapy Evaluation Program
CYP	cytochrome P450
DCO	data cutoff
DILI	drug-induced liver injury
DLBCL	diffuse large B-cell lymphoma
DLT	dose-limiting toxicity
DoR	duration of response
ECG	electrocardiogram
ECHO	echocardiogram
ECOG	Eastern Cooperative Oncology Group

Abbreviation or special term	Explanation
eCRF	electronic case report form
EDC	electronic data capture
EoT	end of treatment
FDA	Food and Drug Administration
FDG	fluorodeoxyglucose
FFPE	formalin-fixed paraffin-embedded
FL	follicular lymphoma
GCP	Good Clinical Practice
HCP	healthcare provider
HL	Hy's Law
HSCT	haematopoietic stem cell transplantation
IC ₅₀	half-maximal inhibitory concentration
ICF	informed consent form
ICH	International Council for Harmonisation
IEC	Independent Ethics Committee
IgG	immunoglobulin G
IgM	immunoglobulin M
IRB	Institutional Review Board
IRT	Interactive Response Technology
IV	intravenous(ly)
LVEF	left ventricular ejection fraction
mAb	monoclonal antibody
MCL	mantle cell lymphoma
CCI	CCI
MRI	magnetic resonance imaging
MTD	maximum tolerated dose
MUGA	multigated acquisition scan
MZL	marginal zone lymphoma
NCI	National Cancer Institute
NHL	non-Hodgkin lymphoma
OAE	other significant adverse event
ORR	objective response rate
OS	overall survival
PBMC	peripheral blood mononuclear cell
PCR	polymerase chain reaction
PD	progressive disease

Abbreviation or special term	Explanation
PET	positron emission tomography
PFS	progression-free survival
PHL	Potential Hy's Law
PK	pharmacokinetic(s)
PR	partial response
RP2D	recommended Phase II dose
R/R	relapsed/refractory
QTcF	QTc corrected by Fridericia's formula
SAE	serious adverse event
SAP	statistical analysis plan
SARS-CoV-2	severe acute respiratory syndrome coronavirus 2
SCT	stem cell transplantation
SD	stable disease
SoA	Schedule of Activities
SRC	Safety Review Committee
TBL	total bilirubin
TLS	tumour lysis syndrome
TPV	third-party vendor
TTR	time to response
ULN	upper limit of normal
US	United States

| 11.7.3 | Clinical Laboratory | 54 |
| 11.7.4 | Vital Signs | 54 |
| 11.7.5 | Electrocardiogram | 54 |
| 11.7.6 | Other Safety Assessments | 54 |
| 12 | INTERIM ANALYSIS – MODULE 1 | 55 |
| 12.1 | Dose Escalation Committee | 55 |
| 12.2 | Interim Analysis | 55 |
| 13 | REFERENCES | 56 |
| 14 | APPENDIX | 57 |

LIST OF ABBREVIATIONS

| Abbreviation or Specialized Term | Definition |
|----------------------------------|--|
| AE | Adverse event |
| ALT | Alanine aminotransferase |
| AST | Aspartate aminotransferase |
| AESI | Adverse event of special interest |
| Bcl-2 | B-cell lymphoma 2 |
| Bcl-xL | B-cell lymphoma-extra large |
| BMI | Body mass index |
| B-NHL | B-cell non-Hodgkin lymphoma |
| CI | confidence interval |
| eCRF | electronic case report form |
| CSP | Clinical Study Protocol |
| CSR | Clinical Study Report |
| COVID-19 | Coronavirus disease 2019 |
| CR | Complete response |
| CT | computed tomography |
| CTCAE | Common Terminology Criteria for Adverse Events |
| CV | Coefficient of variation |
| DCO | Data cut-off |
| DILI | Drug-induced liver injury |
| DLBCL | Diffuse large B-cell lymphoma |
| DLT | Dose-limiting toxicity |
| DoR | Duration of response |
| ECG | Electrocardiogram |
| ECHO | Echocardiogram |
| ECOG | Eastern Cooperative Oncology Group |
| Gmean | Geometric mean |
| ICF | Informed consent form |
| IP | Investigational Product |
| IPD | Important Protocol Deviation |
| ITT | Intent-to-Treat |
| LVEF | Left ventricular ejection fraction |
| MCL | Mantle cell lymphoma |

| Abbreviation or Specialized Term | Definition |
|----------------------------------|--|
| MedDRA | Medical Dictionary for Regulatory Activities |
| MRI | Magnetic resonance imaging |
| MTD | Maximum tolerated dose |
| mTPI-2 | Modified toxicity probability interval |
| MUGA | Multigated acquisition scan |
| MZL | Marginal zone lymphoma |
| NA | Not applicable |
| NC | Not calculable |
| NCI | National Cancer Institute |
| NHL | Non-Hodgkin lymphoma |
| NQ | Non-quantifiable |
| NTLs | Non-target lesions |
| OAE | Other significant adverse event |
| ORR | Objective response rate |
| OS | Overall survival |
| PD | Progressive disease |
| PFS | Progression-free survival |
| PK | Pharmacokinetics |
| PR | Partial response |
| RP2D | Recommended Phase II dose |
| R/R | Relapsed/refractory |
| QTcF | QTc corrected by Fridericia's formula |
| SAE | Serious adverse event |
| SAF | Safety analysis set |
| SAP | Statistical Analysis Plan |
| SD | Stable disease |
| SRC | Safety Review Committee |
| Std Dev | Standard deviation |
| TEAE | Treatment emergent adverse event |
| TLs | Target lesions |
| TLS | Tumour lysis syndrome |
| TTR | Time to response |

AMENDMENT HISTORY

| Category Change refers to: | Date | Description of change | In line with CSP? | Rationale |
|-------------------------------|-------------------------------|-----------------------|-------------------|-----------|
| N/A | Click or tap to enter a date. | Initial approved SAP | N/A | N/A |

